6. GENERAL ANALYSIS DEFINITIONS

6.1 TREATMENT(S)

For basic information on treatment in the study, please refer to NIS Protocol Section 4. The technical specification for treatment set-up is described in the Analysis Data Set (ADS) plan.

For safety analyses, data up to 21 days after last treatment intake during observation period will be considered as on treatment for AE.

6.2 IMPORTANT PROTOCOL VIOLATIONS

The following table defines the different categories of important PVs. The final column describes which PVs will be used to exclude patients from the each patient analysis sets.

Observed PVs will be concluded as important or not important at report planning meetings before database lock at the latest.

Table 6.2:1 Important protocol violations

Category / Code	Description	Requirements	Method	Excluded from
A	Entrance criteria not met			
A1	No COPD(chronic bronchitis, emphysema)		Automated	Effectiveness
A2	Patient received Spiolto Respimat treatment before registration	See Previous Medication code:	Automated	Safety Effectiveness
A3	Patients who have been enrolled this study before		Manual	Safety Effectiveness
A4	Patients who are participating in a clinical trial or registry.		Manual	Safety Effectiveness
B	Contract			
B1	No valid site contract was available		Manual	Safety Effectiveness
C	Trial medication			
C1	No treatment with Spiolto Respimat		Automated	Safety Effectiveness
D	Missing data			
D1	No patient visit after registration	See CRF "Administration status"	Automated	Safety Effectiveness
D2	No CRF after registration		Automated	Safety Effectiveness
D3	No Effectiveness data	No Patient's Global Rating, no Physicians' global assessment and no available change value from baseline of CAT, FEV ₁ and FVC.	Automated	Effectiveness

6.3 PATIENT SETS ANALYSED

The safety set and the effectiveness set are defined as follows. The safety set will be the basis of all demographic, baseline and safety analyses. Effectiveness analysis will be on basis of the effectiveness set.

- Safety set:
This patient set includes all patients who were documented to have taken at least one dose of Spiolto Respimat.
- Effectiveness set:
This patient set is a subset of the safety set that not received Spiolto Respimat patients before registration, and who have change value from baseline at least one CAT, FEV1 and FVC.

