## **9. RESEARCH METHODS**

### **9.1 STUDY DESIGN**

This is an observational study based on newly collect real-world data (i.e., data under real-world practice) to evaluate safety and effectiveness of Tio+Olo FDC 5µg/5µg in patients with chronic obstructive pulmonary disease (chronic bronchitis, emphysema).

The study will be initiated after marketing of Tio+Olo FDC 5µg/5µg in Japan. The study will consist of a baseline visit and further visits in a 52-week follow-up for patients who have initiated the Tio+Olo FDC 5µg/5µg treatment.

As this is an observational study, no specific treatment is mandated or withheld from the patients. The choice of maintenance treatment for chronic obstructive pulmonary disease (chronic bronchitis, emphysema) must be according to regular medical practice and at discretion of physician (i.e., no randomised assignment of patient to treatment [Tio+Olo FDC or other treatment] is performed). In total, approximately 1100 patients are planned to be registered at approximately 200 study sites in the study.

Patients participating in the subsequent follow-up will undergo regular observations. These observations should be reported after 4, 12, 24 and 52 weeks since the initiation of Tio+Olo FDC 5µg/5µg as long as they continue to receive the treatment. Patients will not be followed any longer once they are reported to have discontinued the Tio+Olo FDC 5µg/5µg treatment. Patients who experience adverse events will be followed up until detailed information on the outcome of the adverse event is collected.

The primary outcome of this study is the incidence and exposure-time adjusted incidence rate of adverse drug reactions (ADRs).

The secondary outcome of this study is:

- COPD assessment test (CAT) at 12 weeks.

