## 9.7 DATA ANALYSIS

This is an observational study to collect real-world data (i.e., data under routine medical practice) on safety and effectiveness of Tio+Olo FDC 5µg/5µg treatment. Analyses are descriptive in nature, including confidence intervals. Due to the nature of the observational study, no confirmatory statistical testing is foreseen in this study. Subgroup analyses are also performed if sample size allows.

Per local regulation, any patient who meets one of the following criteria is treated as ineligible for all analyses:

- No safety observation was documented after registration.
- No required registration procedure was followed.
- No valid site contract was available.

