### **9.7.3 Analyses of effectiveness**

For patients' global rating and physicians' global assessment, the frequency of patients with each score will be tabulated.

For CAT, descriptive statistics will be calculated for the total score and the score of each individual component and the changes from scores at week 12 before first administration.

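### SAP 6.3 and exclusion code D3 define the effectiveness set differently, so patients with only a global rating are kept by one rule and dropped by the other

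*SAP*

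**What the plan says.** SAP 6.2 gives Table 6.2:1 the task of deciding set membership: "The final column describes which PVs will be used to exclude patients from the each patient analysis sets". Code D3, which excludes from the effectiveness set, applies to a patient with "No Patient's Global Rating, no Physicians' global assessment and no available change value from baseline of CAT", and likewise none for FEV1 and FVC. One rating of either kind is enough to escape D3.

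SAP 6.3 defines the effectiveness set as a subset of the safety set. It admits patients not treated before registration, "who have change value from baseline at least one CAT, FEV1 and FVC". The two ratings are not mentioned. The same section adds: "Effectiveness analysis will be on basis of the effectiveness set".

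Protocol 9.7.3 plans the rating tables with no condition on change values: "For patients' global rating and physicians' global assessment, the frequency of patients with each score will be tabulated". That section also plans summaries of the CAT scores themselves, in addition to their changes: "descriptive statistics will be calculated for the total score and the score of each individual component". Protocol 9.1 names "COPD assessment test (CAT) at 12 weeks" as the secondary outcome. SAP 4 declares no departure from the protocol's methods, and SAP 6.6 does not impute missing effectiveness data.

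**The concern.** Two passages settle membership of one analysis set and give different answers for a patient who was rated but has no change value. The SAP does not say which prevails.

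The 6.3 condition does not suit the rating tables. Under Protocol 9.3.2 both ratings are made against the day before treatment began, so they need no recorded baseline score. D3 is the code for having no effectiveness data, so the SAP itself counts a rating as effectiveness data.

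Such patients are plausible. Protocol 9.2.2.3 allows registration up to 14 days from the start of treatment where possible, and CAT is not among the registration items. SAP 6.7 requires the baseline value on or before the day of first administration. Spirometry is recorded only where a site has it, so membership under 6.3 can rest on CAT alone. A patient without a baseline CAT can still be rated at weeks 4, 12, 24 and 52.

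At stake is who enters the two rating tables and, in some cases, the 12-week CAT score summary. By the SAP 7 default, percentages are taken over everyone in the set, so the choice of rule affects denominators as well as counts.

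**Working it through.** The plan states no figure on this point, so the check is a count of data patterns.

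**Step 1. Five items, each present or absent:** patient's global rating (PGR), physician's global assessment (PhGA), and change from baseline in CAT, FEV1 and FVC. This gives 2^5 = 32 patterns.

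- D3 drops only the pattern with all five absent: 32 − 1 = 31 kept.
- 6.3, read as at least one change value, drops every pattern with all three changes absent: 2^2 = 4 dropped, 28 kept.
- Both rules together keep 28, so D3's reference to the ratings has no effect.
- Disagreements: 31 − 28 = 3.

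| PGR | PhGA | Any change in CAT, FEV1, FVC | D3 | 6.3 |
|---|---|---|---|---|
| yes | no | no | keep | drop |
| no | yes | no | keep | drop |
| yes | yes | no | keep | drop |
| no | no | no | drop | drop |

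No pattern is kept by 6.3 and dropped by D3.

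**Step 2. Other readings of the loose wording.** With D3 as above, if 6.3 needs all three changes, D3 keeps 27 patterns that 6.3 drops. If 6.3 needs CAT plus one spirometry change, the figure is 19. If D3 is read as dropping anyone who lacks either rating or lacks all change values, D3 becomes the stricter rule and drops 21 patterns that 6.3 keeps. No reading tested makes the two rules agree.

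**Step 3. The 12-week CAT.** Split CAT into baseline, week 12 and any other post-baseline score. With PGR, PhGA, FEV1 change and FVC change this gives 2^7 = 128 patterns. A CAT change needs the baseline and at least one later score.

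- No CAT change: baseline absent (2^2 = 4 combinations) or baseline present with no later score (1), so 5. With no FEV1 or FVC change and 4 rating combinations, 6.3 drops 5 × 4 = 20.
- D3 drops the 5 of these with no rating. Disputed: 20 − 5 = 15; the reverse never occurs.
- A week-12 score is held in 2 of the 5 CAT combinations, both without a baseline. Disputed patterns with a week-12 score: 2 × 3 = 6. Disputed patterns with a week-12 change: 0.
- In all, 6.3 drops 2 × 4 = 8 patterns with a week-12 score and D3 drops 2. Following D3 restores the score only for patients who were also rated.

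**Step 4. The category for not assessable.** Treat PhGA as absent, not assessable, or rated 1 to 3: 3 × 2^4 = 48 patterns. D3 keeps 47 if not assessable counts as data and 46 if it does not. One pattern depends on the answer.

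**Step 5. Scale.** 1% × 1000 = 10 patients. Let f be the share of the D3 version of the set that is disputed, q the proportion of disputed patients in a given rating category, and p the proportion among the rest. The percentage under D3 is (1 − f)p + fq and under 6.3 it is p. The difference, f(q − p), cannot exceed f in size. With f = 1% a table entry moves by at most 1 percentage point.

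**The case against.** The strongest reply is that the two passages can be applied together: the table lists exclusions, 6.3 states conditions for membership, and the result is one set. The safety set is already read that way, since 6.3 asks only for one dose while the table removes further patients. This stands as far as it goes, but the combined rule makes D3's rating clause idle and still removes rated patients from tables that Protocol 9.7.3 plans without that condition.

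Protocol 9.7 says "any patient who meets one of the following criteria is treated as ineligible for all analyses" and lists three criteria. A missing change value is not among them, but neither are D3 or the no-COPD code A1, and the list does not forbid a narrower effectiveness set. This is fair: the list shows only that the protocol does not call for the 6.3 condition.

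SAP 6.4 and 7.6 are not in the public text and could hold a rule for the rating tables. That cannot be excluded, but no visible passage reconciles the two definitions. The report planning meeting before database lock is an opportunity to settle the matter, not a rule that does.

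On size, CAT is scheduled at baseline and every rating visit, and Protocol Annex 3 has site staff check it for completeness. Pattern counts describe logic, not patients. In two of the three disputed patterns the patient holds only one rating, so the other table loses a denominator entry but no rating. The study is descriptive, the ratings are neither primary nor secondary outcomes, and individual values remain in the listings. All of this stands and limits the importance of the point.

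Deleting the rating clause from D3 would also align the texts. It would, but at the cost of dropping patients with usable ratings.

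**Conclusion.** The concern holds. SAP 6.3 and code D3 give different effectiveness sets, and the difference always runs one way under the natural reading: D3 keeps rating-only patients and 6.3 drops them (31 against 28 of 32 patterns). If 6.3 governs, alone or with D3, these patients leave the denominators of both rating tables and the counts for whichever ratings they have. A rated patient with a 12-week CAT but no baseline CAT and no paired spirometry also leaves the CAT score summary.

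The number affected cannot be derived from the documents and may be small. The ADR outcome and the safety set are not affected. The 12-week CAT change is not affected either, provided 6.3 means at least one change value. The conclusion rests on the visible text. It should be corrected, but it does not threaten the main result.

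**What to change.** Reword the effectiveness set in SAP 6.3 to agree with Table 6.2:1: safety-set patients with none of the table's nine effectiveness exclusions (A1 to A4, B1, C1, D1 to D3). At least one post-baseline PGR, physician's global assessment, or change from baseline in CAT, FEV1 or FVC is then enough, joined by 'or' rather than 'and'. As a useful addition, state whether a physician's rating of not assessable counts as effectiveness data when it is the only item.

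The SAP 7 default denominator and its handling of the missing category can stay as they are. The cost is one reworded definition, one clause and one analysis-set flag, with no new data or tables.

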6.5 POOLING OF CENTRES

This section is not applicable because centre/country is not included in the statistical model.

6.6 HANDLING OF MISSING DATA AND OUTLIERS

If only year of date is non-missing, then missing date are imputed 01 JUL of reported year. Else if only year and month of date are non-missing, then missing date is imputed 15 of the reported month.

Safety:

Missing or incomplete AE dates are imputed according to BI standards (see “Handling of missing and incomplete AE dates”). (1)

Effectiveness:

Missing effectiveness data will not be imputed.

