#### **9.2.2.2 Registration period**

From August 2016 to August 2017

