## **9.3 VARIABLES**

### **9.3.1 Exposure**

Exposure to Tio+Olo FDC 5µg/5µg is estimated as time from the day Tio+Olo FDC 5µg/5µg is initiated until the day the drug is last administrated on a patient-level (or the final contact with the patient during the regular observation period).

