 - Baseline FVC [L] pre bronchodilator
 - Baseline %FVC [%]
 - Baseline %FVC [%] post bronchodilator
 - Baseline %FVC [%] pre bronchodilator
 - Baseline EFV₁/FVC [%]
 - Baseline EFV₁/FVC [%] post bronchodilator
 - Baseline EFV₁/FVC [%] pre bronchodilator

- Note:
 - “post bronchodilator”; That fall under any of the following.
 - Use of long-acting bronchodilator within 8 hours before PFT
 - Use of long-acting bronchodilator (twice daily type) within 12 hours before PFT
 - Use of long-acting bronchodilator (once daily type) within 24 hours before PFT
 - ”pre bronchodilator”; That fall under all of the following.
 - Not use of long-acting bronchodilator within 8 hours before PFT
 - Not use of long-acting bronchodilator (twice daily type) within 12 hours before PFT
 - Not use of long-acting bronchodilator (once daily type) within 24 hours before PFT
- note: $\% FEV_1 [\%] = (FEV_1 [L]) / ((0.036: \text{if male}, 0.022: \text{if female}) * (\text{height [cm]}) - (0.028: \text{if male}, 0.022: \text{if female}) * \text{age} - (1.178: \text{if male}, 0.005: \text{if female})) * 100$
- $\%FVC [\%] = (FVC [L]) / ((0.042: \text{if male}, 0.031: \text{if female}) * (\text{height [cm]}) - (0.024: \text{if male}, 0.019: \text{if female}) * \text{age} - (1.785: \text{if male}, 1.105: \text{if female})) * 100$
- (Please refer (2).)
- Pregnancy: Yes, No, Unknown
- Previous medications: Yes, No, Unknown
 - Medication administered from 28 days before administration of Spiolto Respimat to 1 day before administration of Spiolto Respimat.
 - Respiratory medication: Yes, No
 - note: Respiratory medication = LAMA, LABA and/or ICS
 - LAMA monotherapy: Yes, No
 - LABA monotherapy: Yes, No
 - ICS monotherapy: Yes, No
 - ICS+LABA (free combination + fixed dose combination): Yes, No
 - ICS+LAMA (free combination + fixed dose combination): Yes, No
 - LAMA+LABA (free combination + fixed dose combination): Yes, No
 - ICS+LAMA+LABA (free combination + fixed dose combination): Yes, No
 - Other respiratory medication
 - Theophylline: Yes, No
 - Mucolytic: Yes, No
- Concomitant medications: Yes, No, Unknown
 - Respiratory medication: Yes, No
 - note: Respiratory medication = LAMA, LABA and/or ICS
 - LAMA monotherapy: Yes, No
 - LABA monotherapy: Yes, No
 - ICS monotherapy: Yes, No
 - ICS+LABA (free combination + fixed dose combination): Yes, No
 - ICS+LAMA (free combination + fixed dose combination): Yes, No
 - LAMA+LABA (free combination + fixed dose combination): Yes, No

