 - ICS+LAMA+LABA (free combination + fixed dose combination): Yes, No
 - Other respiratory medication
 - Theophylline: Yes, No
 - Mucolytic: Yes, No
- Previous therapy: Yes, No, Unknown

- Concomitant therapy: Yes, No, Unknown

Treatment exposure:

- Duration of Spiolto Respimat treatment [days] = (date of last treatment intake) - (date of first intake) + 1
If after the data lock, Spiolto Respimat is ongoing and date of last treatment intake is missing: date of last treatment intake = Latest date in book
- Duration of Spiolto Respimat treatment class [weeks]: <= 4 weeks, 4 to <= 12 weeks, 12 to <=24 weeks, 24 to <=52 weeks, > 52 weeks.
Note: In terms of days <= 29days, 29 to <= 85days, 85 to <= 169, 169 to <= 365, >365

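### The SAP's 01 July and day-15 date rules have no bounds, so a partial stop date can put the last dose before the first and drop that patient's adverse events

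*SAP*

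**What the plan says.** SAP 6.6 gives a general rule for partial dates. If only the year is known, "then missing date are imputed 01 JUL of reported year". If year and month are known, "then missing date is imputed 15 of the reported month". The one exemption is for adverse events: "Missing or incomplete AE dates are imputed according to BI standards". Nothing ties an imputed date to the first dose, to a visit or to the last contact.

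Three definitions in the SAP depend on such dates:

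- Exposure (SAP 5.4) is computed as "date of last treatment intake) - (date of first intake) + 1". If treatment is ongoing and the last intake date is missing, "date of last treatment intake = Latest date in book".
- The treatment-emergent window (SAP 6.1 and 7.8.1) runs from first intake to 21 days after last intake during the observation period.
- Previous medication (SAP 5.4) is "Medication administered from 28 days before administration of Spiolto Respimat to 1 day before administration of Spiolto Respimat". Protocol 9.3.2 stratifies the safety results by treatment type before baseline.

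Protocol 9.3.1 ends exposure at the last administration or at "the final contact with the patient during the regular observation period". Protocol 6 starts data collection on 23 August 2016, and Protocol 9.2.2.2 sets registration as "From August 2016 to August 2017".

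**The concern.** A mid-year or mid-month default is harmless only if it is then checked against dates that are known. Here enrolment opens after 01 July 2016, so the year-only rule cannot give a possible stop date in 2016.

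Exposure is the denominator of the primary rate, and last intake closes the window that decides which adverse events count. A patient with an impossible stop date still counts in the safety set of SAP 6.3, but without events. Stop dates matter mostly for patients who discontinued, and Protocol 9.3.2 names adverse events leading to discontinuation as an outcome. Imputed prior-drug dates can also put a patient in the wrong prior-treatment stratum.

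**Working it through.** **The plan's own figures.** SAP 5.4 gives exposure classes ending at 29, 85, 169 and 365 days. These equal 7 × weeks + 1 for 4, 12, 24 and 52 weeks, so they reproduce exactly.

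**Year-only stop in 2016.** The imputed last intake is 01 July 2016, and duration = last - first + 1.

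- First dose 23 August 2016: -53 + 1 = -52 days.
- First dose 31 December 2016: -183 + 1 = -182 days.
- Window end: 01 July + 21 days = 22 July 2016, before any first dose. The window is empty.
- Protocol 9.2.2.3 allows registration within 14 days of starting, so a first dose could be as early as 10 August 2016. That still gives -40 + 1 = -39 days.

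**Year-only stop in 2017.** For a first dose on 2 July 2017, -1 + 1 = 0. For 31 August 2017, -61 + 1 = -60 days. A stop in the same year is impossible for every first dose from 2 July 2017.

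**Month-only stop in the month of first dose.** First dose on day 16: 15 - 16 + 1 = 0. First dose on day 31: 15 - 31 + 1 = -15 days. Here the 21 days carry the window past first dose, so it is shortened but not empty.

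**Share affected, given a partial stop date.** The assumptions are first doses evenly spread over the 374 days from 23 August 2016 to 31 August 2017, and true stops evenly spread over the days shown.

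| | Stops over day 1-28 | Stops over day 1-365 |
|---|---|---|
| Year-only, duration 0 or less | 48% | 13% |
| Month-only, duration 0 or less | 15% | 1% |

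With stops over day 1-365, the exposure class is wrong in 63% of year-only and 8% of month-only cases, counting non-positive durations as wrong. The error runs from -183 to +181 days for year-only dates and from -16 to +14 days for month-only dates.

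**Effect on the whole cohort.** Assume 1000 patients, 20% to 40% stopping early, and 2% to 10% of those stop dates year-only. Expected patients with non-positive exposure are 1000 × 0.20 × 0.02 × 0.13 = 0.5 up to 1000 × 0.40 × 0.10 × 0.13 = 5.2. In simulation, total patient-years (about 800 to 900) change by less than 0.02%, because early and late errors cancel.

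Lost and gained events need not cancel. Protocol 11.2 collects adverse events only to 21 days after last intake, so a stop placed too late can add few events. A stop placed too early removes real ones.

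**Prior treatment.** Take a drug truly stopped the day before first Spiolto intake, with a year-only stop date. Over the 374 first-dose dates:

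- 165 (44%) put the stop before day -28, so the drug leaves the window.
- 181 (48%) put the stop on or after first Spiolto intake, so the drug appears to overlap treatment.
- 28 (7%) stay inside the window.

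With a month-only stop date, none leave the window and 45% fall on or after first intake. Start dates are exposed too. If Spiolto begins on 1 March 2017, a prior drug begun that January but recorded only as 2017 is given a start of 01 July, 122 days after first intake.

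**Ongoing treatment.** Day 365 is 22 August 2017 for a first dose on 23 August 2016, and 30 August 2018 for one on 31 August 2017. Data collection ends on 30 November 2018, which is day 830 and day 457 respectively. A date in the book could therefore fall after the regular 52 weeks, if dates other than visits count.

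**The case against.** Partial Spiolto stop dates should be uncommon. The start date is a required registration item, administration is recorded throughout, visits fall at 4, 12, 24 and 52 weeks, and data are transmitted at discontinuation (Protocol 9.1, 9.2.2.3, 9.4, Annex 2). This stands. The percentages above are shares of partial dates, not of patients.

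Bounds may also exist in the analysis data set plan, to which SAP 6.1 refers and which is not available here. That is possible. But SAP 3 says the document gives the detailed procedures, and SAP 6.6 states an explicit rule without pointing elsewhere. The restriction of last intake to the observation period in SAP 6.1 and 7.8.1 supplies neither a lower bound nor a rule for what to do when it is breached.

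On prior treatment, SAP 5.4 counts drugs administered in the window. A drug with a known stop date before Spiolto might be kept whatever its imputed start. This also stands, so the problem is limited to cases that the imputed dates decide. It comes from the medication dates, not from a misplaced last Spiolto dose.

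A reader might infer that the rule for ongoing treatment inflates exposure, and only in patients with adverse events. The documents do not support that. The date is a recorded one, so it cannot precede first dose in a followed patient. Protocol 9.4 defines the books by visits. Concomitant drugs and therapies are also recorded throughout, so late dates would not be confined to patients with events. The SAP also plans an exposure class above 52 weeks. What remains is that SAP 5.4 omits the limit in Protocol 9.3.1 and does not say which dates count.

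**Conclusion.** The point holds, at minor severity. Read as written, SAP 6.6 gives an impossible result for every Spiolto stop recorded only as 2016 and for some month-only stops. It can also misplace prior-drug dates. The harm is lost adverse events and wrong exposure classes in a few patients.

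A reader might go further and infer that the primary rate is corrupted. The figures do not support that: patient-years barely move. Even if all of about 5 affected patients had an adverse drug reaction and lost it, incidence would fall by 5/1000 = 0.5 percentage points.

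These sizes rest on assumed frequencies of early stopping and of partial dates, on even start and stop times, and on no bound being set in the analysis data set plan. The ongoing-treatment rule is a matter of alignment with the protocol, not a demonstrated error.

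**What to change.** In SAP 6.6:

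- Bound an imputed last-intake date below by first intake and by the last visit at which treatment was recorded as ongoing. Bound it above by the date discontinuation was reported or the last contact in the regular observation period. For a first dose on 23 August 2016 and a stop recorded as 2016, the first-intake bound and the end of the year alone limit duration to 1 to 131 days, instead of -52.
- Do not let the imputed start or stop of a drug known to have been used before Spiolto fall on or after first Spiolto intake.
- If the analysis data set plan already holds such bounds, cite it instead.

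In SAP 5.4, state that the date used for ongoing treatment is the last contact in the regular observation period, as in Protocol 9.3.1, and not an adverse event follow-up date.

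The cost is a few sentences and a few lines of code. No new data are needed, and no endpoint or analysis set definition changes.
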